The experimental research measures in this project will not directly benefit the participants, other than the knowledge that they are contributing to our understanding of the underlying factors that may cause treatment-resistance to previous treatments and may provide insight into a novel medication-enhanced psychotherapy and thus, there is a benefit of contribution to society. In the therapy portion of the project, it is also possible that participants may experience improved symptoms of depression, mood, anxiety, as well as reduced tendencies of HPM/OC. As part of the ketamine treatment, participants may also experience improved symptoms of depression and anxiety. There is a possible effect that the combination of ketamine and RO DBT will be especially beneficial in combination, although this is unknown, as it is a goal of the study to test the combined treatment. As mentioned above, measures are being taken to minimize any potential risks.

E Study Design

E1 Overview or Design Summary

Eligible patient (n=15) young adults will attend a baseline session where they will undergo an ERP neural assessment and fill out questionnaires. Then, participants will complete 4 weeks of ketamine and 4 months of RO DBT. Participants will start with 2 weeks of individual therapy (RODBT) to orient to therapy and infusion protocols. Then, participants will complete a 4-week course of twice weekly 40-minute ketamine infusions administered 6-24 hours prior to RO DBT psychotherapy (also when RO DBT group therapy will commence). Following completion of the 4-week ketamine-enhanced RO DBT, participants will complete another in-person session with an EEG and behavioral assessment. Next, participants will continue to complete RO DBT treatment of individual and group treatment for an additional 16 weeks. At the end of this treatment, participants will complete a third session where they will undergo an ERP neural assessment and fill out questionnaires. Participants will also complete self-reported questionnaires following each ketamine and RO DBT

session (4 weeks) and weekly self-reported questionnaires during non-ketamine RO DBT.

E2 Subject Selection and Withdrawal

2.a Inclusion Criteria

Young adults with treatment-resistant depression: Inclusion criteria:

- Males and females aged 18-65

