Re: Therapy and ketamine trial-- Participants are not randomized. They will be fully informed of the free therapy and ketamine trial and will not be coerced into it. Free therapy and ketamine will be provided to all patients (as this is a feasibility and acceptability study). If any patient participating in the study needs a higher level of care, they will immediately be removed from the treatment protocol and will be coordinated with other providers to ensure they get the care necessary. If any patient participating in the study decides they no longer want to be in the trial, they can end at any point and it will be coordinated to help them continue treatment with other providers.

Re: experimental session—all participation is voluntary, including answering questions and participating in the ERP.

2.c Subject Recruitment Plans and Consent Process

Study population:

Young adults age 18-65 years with TRD who exhibit HPM/OC.

Consent process: If an interested participant contacts the research team about the study, a member of the research team will provide information about the study and required elements of consent over the telephone (see attached “Consent for Phone Screen”) prior to obtaining the participants verbal consent to participate in the screening elements of the study. This phone screen will allow possible participants to ask questions and clarifications prior to coming in person for the in-person consent process (and includes the child having the opportunity to ask questions). If a participant meets eligibility criteria for enrollment in the study based on their Initial Phone/Exclusion Screen and the participant indicates they wish to continue with the study, the participant will receive an email to complete the a measure of HPM/OC, the Word Pairs Checklist. The participant must consent to complete these questionnaires. If the participant is eligible following completion of the phone screen and questionnaires, the research team will notify the participant of their eligibility and ask whether they want to continue with the study. If the participant is unsure, the research assistant will provide

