Using G*Power, power for Aim 1 (MDD symptoms) was based on a) a pilot of RODBT from the PI, b) Lynch et al. (2020),⁽⁹⁾ a multi-site RCT of RODBT in TRD and c) Zarate et al (2006)⁽³⁷⁾, an original RCT of ketamine in TRD. With $\alpha=.05$ and power of 80%, we would need a sample of 8 to detect an effect from RODBT, and $n=5$ with ketamine. For Aim 2, we used a) Baudinet et al (2021)⁽¹¹⁾ who tested RODBT change in behavioral flexibility and reward processing and b) a pilot of RODBT from the PI. With $\alpha=.05$ and power of 80%, we would need a sample of 5-15 participants to detect behavioral change in mechanistic process. Power for neural change in HPM/OC has not been computed because no previous studies have targeted HPM/OC with ketamine. However, our sample is similar to other medication-assisted psychotherapy pilot studies.

G2 Interim Monitoring and Early Stopping

This is part of Analysis 1a below. Specifically, side effects and symptoms will be monitored at each ketamine and RO DBT session for 4 weeks while they are running concurrently. If there are any issues with running a ketamine session and a psychotherapy session within 1-2 days of each other, protocols can be modified or stopped, if necessary.

G3 Analysis Plan

Analysis 1a: No analyses will be completed for H1a; qualitative data from session questionnaires regarding side-effects, symptoms and functioning will be continually monitored, to assess if there is a need to modify protocols. **H1b:** Using individual session data, ketamine will catalyze psychiatric symptom change in RODBT and ketamine-enhanced RODBT will be associated with decreasing trajectories of depressive symptoms. Analysis 1b: Multilevel linear modeling (MLM) with random intercepts and slopes will model trajectories of depressive symptoms across treatment.

Aim 2: Examine preliminary efficacy of ketamine-enhanced RODBT in engaging neural and behavioral mechanistic targets in young adults with

moderate to severe depression.

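### The Aim 1 sample sizes come from separate studies of RODBT and of ketamine, so G1 gives no power for the H1b clause that ketamine catalyzes change in RODBT

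*Combined protocol and SAP*

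**What the plan says.** G1 (Sample Size Determination and Power) labels its first calculation as power for Aim 1, depressive symptoms. It names three sources: "a pilot of RODBT from the PI", "a multi-site RCT of RODBT in TRD" and "an original RCT of ketamine in TRD". At alpha .05 and 80% power the result is "we would need a sample of 8 to detect an effect from RODBT", and n=5 for ketamine. No effect size, standard deviation, test or sidedness is given. Later in G1 the plan says openly that power was not computed for neural change under Aim 2. It makes no such statement about any part of Aim 1.

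H1b, repeated in A2, C1 and G3, has two clauses: "ketamine will catalyze psychiatric symptom change in RODBT and ketamine-enhanced RODBT will be associated with decreasing trajectories of depressive symptoms". Analysis 1b in G3 is one multilevel model with random intercepts and slopes for depressive symptoms across treatment. It names no ketamine, phase or infusion-timing term.

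The design has a single group. E1 states: "Eligible patient (n=15) young adults will attend a baseline session". Section 2.b (Ethical Considerations) says that there is no randomization and adds: "Free therapy and ketamine will be provided to all patients (as this is a feasibility and acceptability study". E1 also sets the sequence: two weeks of individual RODBT, four weeks of twice-weekly infusions with RODBT, then RODBT without ketamine.

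**The concern.** A power statement covers only the effect put into it. G1's inputs are an RODBT effect and a ketamine effect, from different studies. The catalysis clause is a contrast: symptom change in RODBT with ketamine against change in RODBT without it. Full disclosure of the G*Power settings would not close this gap, because 8 and 5 would still answer another question.

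A reader who sees 8, 5 and a planned 15 under the Aim 1 label will probably conclude that Aim 1 is comfortably powered throughout, all the more because G1 does flag the neural outcomes as not powered. Catalysis is not a side issue. A3 gives it as part of the study's purpose, and B1 lists testing it as a goal. If the implied 80% is carried over to that clause, a null result could be misread as evidence that ketamine adds nothing to RODBT.

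**Working it through.** **1. Can 8 and 5 be reproduced?** No. G1 gives alpha (.05), power (80%) and the answers (8 and 5), but not the effect sizes or the test. The most that can be done is to solve backward under an assumed test.

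**2. Effects implied by 8 and 5.** Assume a one-sample or paired t-test on within-person change, with dz = mean change / SD of change. Two-sided power is

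power = P(|T| > t(0.975, n−1)), where T is noncentral t with n−1 degrees of freedom and noncentrality dz·√n.

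Setting power to 0.80 and solving for dz:

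| n | dz, two-sided | dz, one-sided |
|---|---|---|
| 8 | 1.16 | 0.98 |
| 5 | 1.68 | 1.36 |
| 15 (planned) | 0.78 | 0.68 |

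For n=15, for example, dz·√n = 0.778 × 3.873 = 3.01.

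The backward solution depends on the assumed test. If 8 and 5 were sizes per arm in a two-group t-test, the implied standardized differences would be 1.51 and 2.02. Two of G1's three sources are described as RCTs, so that reading cannot be ruled out.

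**3. What n=15 gives if those effects carry over to overall decline.** Under the paired two-sided reading, power at n=15 is about 99% for dz 1.16 and above 99.9% for dz 1.68. In this sense G1 loosely supports the second clause of H1b.

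**4. What n=15 gives for catalysis.** The documents state no incremental effect, so the values below are assumptions. Same test, two-sided, alpha .05:

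| Assumed dz of the within-person contrast | Power at n=15 | n for 80% power |
|---|---|---|
| 0.3 | 19% | 90 |
| 0.5 | 44% | 34 |
| 0.6 | 58% | 24 |
| 0.8 | 82% | 15 |

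The 80% threshold at n=15 is dz of about 0.78. All 15 participants are taken to contribute. The documents give no dropout rate, and any loss would raise the threshold.

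**5. Status of these figures.** They describe one paired contrast per person. Analysis 1b is a multilevel model on repeated session data and defines no ketamine contrast, so its power for catalysis cannot be computed from the documents. The 0.78 shows the order of magnitude only.

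**The case against.** The case for leaving G1 alone has force. G1 never says in words that it has 80% power for catalysis. It speaks of an RODBT effect and a ketamine effect under a depressive-symptoms label, and the decline clause of H1b is roughly what those inputs address. The study is an unrandomized feasibility pilot with preliminary aims, the sample is set at 15, and nothing in the plan depends on a catalysis power figure. All this limits the consequence. It does not remove the mismatch: the calculation is offered for Aim 1, H1b is an Aim 1 hypothesis, and only the neural outcomes carry a caveat.

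Several stronger readings are tempting, and the documents do not support them:

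- *That 8 or 5 is miscalculated.* Neither can be checked without the omitted inputs. The defect is one of scope.
- *That the added effect of ketamine must be smaller than either single-treatment effect.* No incremental effect is given, and the Benefits text in D1 calls any special benefit of the combination unknown. The defensible statement is that it is a different quantity and is not shown to be as large.
- *That 8 and 5 are pre-post changes under each treatment alone.* G1 does not state the type of effect, and some may be between-arm contrasts.
- *That 0.78 is the smallest effect the planned model can detect.* It holds only for the assumed paired test.

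In the other direction, the n=5 could be read as RODBT combined with ketamine. G1's only ketamine source is described as a trial of ketamine, so the more natural reading is a ketamine effect.

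**Conclusion.** The point holds as one about scope. The stated Aim 1 power does not extend to the first clause of H1b, and G1 does not say so. This follows from G1's own description of its sources and from the single-group design, and needs no assumption about effect size.

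The size of the gap does rest on assumptions. With a two-sided paired t-test at alpha .05 and all 15 participants analysed, power for catalysis ranges from 19% to 82% over assumed dz of 0.3 to 0.8. A catalyst effect of moderate size could easily be missed. The trial itself is not put in doubt: a small pilot is legitimate, but it should not appear to have power that it has not computed.

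**What to change.** **In G1**, state that 8 and 5 derive from separate RODBT and ketamine studies, give the effect size, test and sidedness behind each, and state that no power was computed for the catalysis clause of H1b, as is already done for neural change. If a benchmark is wanted, give dz of about 0.78 at n=15 and label it as based on an assumed two-sided paired t-test, not on the multilevel model.

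**In Analysis 1b**, define the within-person contrast that addresses catalysis. One option is the PHQ-9 slope in the ketamine weeks against the slope in the RODBT-only weeks already in the design. Report it as an exploratory estimate with a 95% confidence interval. All participants pass through the phases in the same order, so the contrast is mixed with time in treatment, which is a further reason to call it exploratory. E1 plans weekly questionnaires during RODBT without ketamine, but F2 names the PHQ-9 weekly only after the ketamine portion. The plan should confirm which RODBT-only weeks supply PHQ-9 data.

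**Cost:** a less favourable power statement and one added model term. Sample size and visits do not change.

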Medication-assisted psychotherapy: Using ketamine-enhanced RODBT to target neural and behavioral mechanisms of action in emerging adults with moderate to severe depression

Principal Investigator: [name]

NCT Number: NCT06138691

Version Date/Number: Version 7-- 9/26/25

A Introduction

A1 Study Abstract

Heightened performance monitoring and overcontrol (HPM/OC) is a transdiagnostic phenotype characterized by checking behaviors, cognitive inflexibility/rigidity, and social concern/perfectionism and underlies treatment resistant depression (TRD). TRD presents a sizeable public health concern with higher hospitalizations, suicide, disability and mortality rates compared to major depression, and \$44 billion yearly in societal cost. The goal of this project is to examine feasibility and efficacy of a cutting-edge medication-assisted psychotherapy, ketamine-enhanced Radically Open Dialectical Behavior Therapy (RODBT) in 15 emerging adults with moderate to severe depression. We aim to test whether ketamine-enhanced RODBT targets the purported mechanism of action, HPM/OC. RODBT alone has not enacted neural change and ketamine may prove as a catalyst to treatment-response. Given the current mental health crisis, only exacerbated by COVID-19, synergistically targeting TRD with fast-acting (ketamine) and durable (RODBT) mechanistic treatment, early in the developmental course, is imperative in lessening the lifelong burden of psychiatric illness.

A2 Primary Hypothesis

Aim 1: Examine preliminary feasibility and efficacy of ketamine-enhanced RODBT. Hypothesis 1a: Ketamine infusions 1-2 days prior to RODBT psychotherapy sessions will be well-tolerated and feasible. Hypothesis 1b: Using individual session data, ketamine will catalyze psychiatric symptom change in RODBT and ketamine-enhanced RODBT will be associated with decreasing trajectories of depressive symptoms.

Aim 2: Examine preliminary efficacy of ketamine-enhanced RODBT in engaging neural and behavioral mechanistic targets in young adults with moderate to severe depression. Hypothesis 2a: Ketamine-enhanced RODBT will be associated with neural ERN reductions and neural RewP increases. Hypothesis 2b: Ketamine-enhanced RODBT will be associated with behavioral cognitive flexibility, openness, reward responding and social functioning improvements.

A3 Purpose of the Study Protocol

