Given TRD is characterized by chronicity and high societal cost^(6,7), effectively treating it early in its' course is imperative for lessening burden over the lifespan. TRD has earlier onset than treatment-responsive MDD, thus, persistent moderate to severe depression during emerging adulthood may be an early manifestation of TRD and a window of opportunity for early intervention.⁽⁴⁾ Moreover, since the start of the COVID-19 pandemic, MDD rates have significantly increased, especially for individuals under age 40 and students.⁽²³⁾ Thus, given the current mental health crisis, targeting TRD with fast-acting *and* durable mechanistic treatment at the earliest developmental timepoint is imperative. The current research team brings together relevant expertise across adolescent/young adult ([name], [name]) and adult ([name], [name]) populations to conduct highly innovative medication-assisted psychotherapy research that could profoundly impact new lines of treatment research. The current project brings together this distinct expertise into a novel collaboration that we have reason to believe may synergistically lead to both fast-acting (ketamine) and also longer-

lasting (RODBT) mechanistic change in a highly treatment- resistant psychiatric presentation that demonstrates increased prevalence during the transition into adulthood.

C Study Objectives

C1 Primary Aim

Aim 1: Examine preliminary feasibility and efficacy of ketamine-enhanced RODBT. Hypothesis 1a: Ketamine infusions 6-24 hours prior to RODBT psychotherapy sessions will be well-tolerated and feasible. Hypothesis 1b: Using individual session data, ketamine will catalyze psychiatric symptom change in RODBT and ketamine-enhanced RODBT will be associated with decreasing trajectories of depressive symptoms.

C2 Secondary Aim

Aim 2: Examine preliminary efficacy of ketamine-enhanced RODBT in engaging neural and behavioral mechanistic targets in young adults with moderate to severe depression. Hypothesis 2a: Ketamine-enhanced RODBT will be associated with neural ERN reductions and neural RewP increases. Hypothesis 2b: Ketamine-enhanced RODBT will be associated with behavioral cognitive flexibility, openness, reward responding and social functioning improvements.

C3 Rationale for the Selection of Outcome Measures

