The outcome measures of neural and behavioral HPM/OC and neural reward and social responding have been chosen to assess the purported underlying mechanisms of change contributing to symptom presentations. We also included functioning and psychiatric symptoms to assess whether targeting a mechanism also influences symptom presentation.

D Investigational Agent

D1 Dose Rationale and Risk/Benefits

Details of Infusion

To ensure dose accuracy, participants will have weight confirmed prior to each infusion. All female participants will complete a urine pregnancy test immediately prior to their first ketamine infusion and will be informed that it is not advised to have unprotected sex throughout the ketamine infusion period (1 month). After safety ratings (see table below) are performed, an IV line will be inserted into upper extremity by research personnel. The ketamine will be infused using an IV infusion pump at a rate of 0.5 mg/kg of body weight over 40 minutes. Heart rate, blood pressure, and pulse-oximetry will be routinely monitored throughout the infusion and for approximately up to two hours after the end of the infusion. Safety ratings will be repeated prior to discharge. After normalization of any psychotomimetic symptoms or blood pressure elevation and IV removal, participants will be discharged.

Direct physical or psychological risks are minimal in the administration of behavioral and electrophysiological measures. Individual psychosocial therapy sessions can elicit some psychological distress while group sessions can elicit some psychological distress or social anxiety. Behavioral tasks can lead to some concern of performance or frustration. Additionally, participants may become bored or tired during the experimental sessions. Some mild discomfort may be associated with the application of the miniature surface electrodes and when skin is mildly abraded. At no time will subjects be coerced to participate in any aspect of testing, subjects will be told that at any time they wish to terminate the experiment or therapy, they are free to do so. There is also always a risk of loss of confidentiality; although this risk is minimal given data are stored electronically behind Washington University's firewall. Lastly, there is a risk of time burden.

Risks of Ketamine infusion:

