unlimited time for the participant to consider whether they would like to participate in the study and a research assistant will notify the participant they can contact the research team if they would like to potentially participate in the future (they may have to re-complete the phone screen at that future time). If the person is still interested, the research team will schedule an in-person session.

The consent process will take place in person at Washington University in St. Louis Department of Psychiatry in a private room with a research team member. The consent process will include providing ample time for the young adult to read/review the consent form. This consent will consent for the experimental sessions and the free ketamine and therapy portion. There is no randomization: if an potential patient participant is interested in the free ketamine/therapy, they can participate in that until we have 15 participants in the therapy portion. A trained research assistant will also discuss the procedures of the study and will answer any questions the participant may have prior to signing. Research team members will remind participants that their participation is completely voluntary and they can choose to withdraw at any time.

2.d Early Withdrawal of Subjects

Participants can withdraw at any point if they desire. Participants in need of higher levels of care will be withdrawn by the PI if medically/psychologically unstable or if they express active suicidal ideation.

2.e When and How to Withdraw Subjects

Participants in need of higher levels of care will be withdrawn by the PI at any point if medically/psychologically unstable or if they express active suicidal ideation and need to be hospitalized. If a participant desires to withdraw, as soon as they inform the study team, the team will remove the participant from current and future study procedures.

2.f Data Collection and Follow-up for Withdrawn Subjects

Data will not be collected for withdrawn subjects once they withdraw. Follow-up for withdrawn subjects will not be done, unless the patient reaches out to us and would like to continue the therapy or study. At this point they would sign another consent form to agree to their continued participation.

F Study Procedures

F1 Screening for Eligibility

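### G3 plans no analysis of H1a, so the first hypothesis under the primary aim has no prespecified quantitative summary of feasibility or tolerability

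*Combined protocol and SAP*

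**What the plan says.** The hypothesis appears twice. A2 words H1a as "Ketamine infusions 1-2 days prior to RODBT psychotherapy sessions will be well-tolerated and feasible". C1, under the primary aim, words it as "Ketamine infusions 6-24 hours prior to RODBT psychotherapy sessions will be well-tolerated and feasible". Section 2.b explains why every participant is treated, without randomisation, "as this is a feasibility and acceptability study".

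For Analysis 1a, G3 says "No analyses will be completed for H1a; qualitative data from session questionnaires regarding side-effects, symptoms and functioning will be continually monitored", and gives the purpose as deciding whether protocols need changing. G2 refers to the same monitoring during the four concurrent weeks and allows modification or stopping, with no numerical rule. G4 only refers back.

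The data go beyond the qualitative. The ketamine session questionnaires in F2 include the KetRO Clinical Events Checklist, the BPRS positive-symptom subscale (BPRS+) and a modified CADSS. D1 has safety ratings before each infusion and adds "Safety ratings will be repeated prior to discharge". It points to a table for them, and the readable text does not show which scales they are.

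On delivery, E1 says "participants will complete a 4-week course of twice weekly 40-minute ketamine infusions administered 6-24 hours prior to RO DBT psychotherapy". On withdrawal, 2.f says "Data will not be collected for withdrawn subjects once they withdraw".

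**The concern.** A feasibility study should end with a statement of how many people could be treated as planned and how many tolerated it. Under G3 as written, nothing prespecified could support or contradict H1a. Any summary would be chosen after the data had been seen, including its denominator and its unit (participants or infusions), and these choices can change the message.

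The participants who stop are the most informative for H1a. E1 places two weeks of individual therapy before ketamine, so someone can enter treatment and leave before the first infusion. If the denominator is not fixed, such a person can drop out of the feasibility result unnoticed.

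**Working it through.** **1. Does another section supply the summary?** The plan gives no figure for H1a, so there is none to reproduce.

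- G1: the Aim 1 sample sizes (8 for RODBT, 5 for ketamine) concern depressive symptoms, which is H1b.
- G2: supports a decision about conduct and produces no estimate.
- G3, Analysis 1b: a multilevel model of depressive symptoms, again H1b.
- G4: adds nothing.
- F2, Therapy: the interviews with completers and dropouts ask about experience and perceived outcome. They do not count delivery or adverse effects.

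None of these fills the gap.

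**2. What could 15 participants show?** Inputs: n = 15 (E1); two infusions a week for 4 weeks (E1), so 2 × 4 = 8 per participant and 15 × 8 = 120 in all. The event counts below are illustrative, because the documents give no event or dropout rates.

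Exact (Clopper-Pearson) 95% limits for x of n: the lower limit is the 0.025 quantile of Beta(x, n − x + 1), and the upper limit is the 0.975 quantile of Beta(x + 1, n − x). At the extremes these reduce to:

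- x = 0: upper limit = 1 − 0.025^(1/15) = 1 − 0.782 = 21.8%
- x = 15: lower limit = 0.025^(1/15) = 78.2%

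| Illustrative result | Proportion | Exact 95% CI |
|---|---|---|
| 0/15 stop for an adverse effect | 0% | 0 to 21.8% |
| 2/15 stop for an adverse effect | 13.3% | 1.7 to 40.5% |
| 12/15 receive all administrations | 80% | 51.9 to 95.7% |
| 15/15 receive all administrations | 100% | 78.2 to 100% |

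If fewer than 15 receive ketamine, the tolerability intervals widen. With 12, zero events gives 1 − 0.025^(1/12) = 26.5%.

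**3. Why participants and not infusions as the unit?** The 120 infusions are clustered within 15 people. An event at 12 of 120 infusions is 10% per infusion. At 8 infusions each, those 12 could come from as few as 2 participants (12/8 = 1.5, rounded up; 2/15 = 13.3%) or as many as 12 (12/15 = 80%).

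**4. Which counts depend on conflicting statements?**

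- Infusion-to-session interval: 1–2 days in A2, F2 (Ketamine protocol) and G2; 6–24 hours in C1 and E1. This affects only an adherence summary.
- Length of RODBT: after 2 weeks of individual therapy and 4 weeks with ketamine, E1 says "participants will continue to complete RO DBT treatment of individual and group treatment for an additional 16 weeks", which adds up to 2 + 4 + 16 = 22 weeks. B1 and F2 (Therapy) give about 16 weeks; D1 and an earlier sentence of E1 give four months. This affects only RODBT completion and attendance.
- Starting ketamine, receiving 8 administrations, checklist events, stopping for an adverse effect and worst scale scores depend on neither.

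**The case against.** The strongest reply is that this is a 15-person single-arm pilot, that side effects are watched at every session, and that formal inference would be pointless. Much of that stands. No hypothesis test is needed and a success threshold is optional. The intervals above reflect n = 15 and would be as wide under any plan, so they do not measure the defect. Counts with stated denominators would close most of the gap; the exact intervals are a cheap addition that keeps the imprecision visible. None of this removes the need to say in advance what will be counted and among whom.

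Several stronger readings are tempting, and the documents do not support them.

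- A reader might infer that side effects will be ignored or go unreported. G3 says only that no analyses will be completed. Monitoring is planned and the scales are collected.
- A reader might infer that nothing can be specified until the interval and duration conflicts are settled. The infusion and tolerability counts depend on neither.
- A reader might treat whole-course RODBT completion as part of H1a. H1a concerns infusions before sessions; RODBT completion belongs to Aim 1's broader feasibility.
- A reader might infer that G5 would remove people who stop. G5 concerns missing outcome data, and a participant who stops has a known completion status. Stating the denominator is a precaution.

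**Conclusion.** The gap is real, and G3 states it outright: the first hypothesis under the primary aim has no prespecified quantitative summary, although usable data are collected. The plan should be changed. Participant safety monitoring, Analysis 1b and the Aim 2 analyses do not depend on this change.

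The size of the gap cannot be given as a bias or a loss of power. What can be shown is what 15 participants support: an upper limit of 21.8% when no one has an event, and a lower limit of 78.2% when everyone completes. An unquantified statement that treatment was well tolerated would hide both. These figures assume that all 15 enter the denominator and that participants are independent units.

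**What to change.** Replace the G3 sentence with a descriptive analysis, with no hypothesis test and with participants as the unit.

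- **(a) Feasibility, among all who start RODBT:** number and proportion (exact 95% CI) who start ketamine and who receive all 8 planned administrations. Show intramuscular administrations, which F2 allows, separately. Those who stop stay in the denominator as not completed.
- **(b) Tolerability, among all who receive at least one administration:** number and proportion (exact 95% CI) with each checklist event at any administration, and who stop ketamine for an adverse effect; median and range of each participant's worst post-infusion CADSS and BPRS+ score; and the number who used as-needed clonidine, since F2 allows it to prevent distressing symptoms. Use worst scores and not change, unless pre-infusion scores on these scales are confirmed.
- **(c) Extensions for Aim 1's broader feasibility, labelled as outside H1a:** RODBT completion, session attendance and completion of the post-treatment assessment.
- **(d) Adherence to the infusion-to-session interval,** summarised per participant.

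Items (a) and (b) can be written now. Item (d) needs the interval statements reconciled first. In (c), only RODBT completion and attendance need the duration statements reconciled. Which statement is right is for the investigators to settle.

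Cost: SAP wording, one or two tables, attendance and interval taken from visit records, and the reason for stopping noted at the time of withdrawal, because 2.f ends data collection then. The checklist and scales are already planned. The downside is that wide intervals will be shown openly.
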